7.4 Outcome Measures

Primary Outcome:

The primary outcome is ventilator-free days (VFDs) to study day 28. VFDs will be defined as the number of calendar days alive and free of invasive mechanical ventilation from the final receipt of invasive mechanical ventilation through 28 days after enrollment. For the assessment of VFDs, the day of enrollment (defined as the day on which the patient first receives invasive mechanical ventilation in a participating study location), will be considered to be day 0. Outcome ascertainment will cease at the time of hospital discharge or 28 days after enrollment, whichever occurs first. Receipt of invasive mechanical ventilation will be considered to end when patients undergo the final tracheal extubation or disconnection of the ventilator from the endotracheal tube or tracheostomy tube between enrollment and 28 days after enrollment. Patients who continue to receive invasive mechanical ventilation at day 28 will receive zero VFDs. Patient who die prior to day 28 will receive zero VFDs. Patients who are discharged from the hospital prior to day 28 and are receiving invasive mechanical ventilation at the time of discharge will receive zero VFDs. Patients who are removed from invasive mechanical ventilation and are discharged from the hospital without invasive mechanical ventilation prior to 28 days will be assumed to remain free of invasive mechanical ventilation between hospital discharge and day 28. For patients who are removed from invasive mechanical ventilation, return to invasive mechanical ventilation, and are subsequently removed again from invasive mechanical ventilation prior to day 28, VFDs will be counted from the final receipt of invasive mechanical ventilation prior to day 28. We chose VFDs as the primary outcome for the PILOT trial as choice of SpO_2 target may simultaneously affect both mortality and duration of invasive mechanical ventilation.

Secondary Outcome:

The sole pre-specified secondary outcome is 28-day in-hospital mortality, defined as death from any cause between enrollment and the first of hospital discharge or 28 days after enrollment.

Exploratory Clinical Outcomes:

1. ICU mortality
2. Vasopressor-free days
3. Renal replacement therapy-free days
4. ICU-free days
5. Hospital-free days

Exploratory Organ Function Outcomes: (All exploratory organ function outcomes will employ only laboratory values and imaging obtained as a part of routine clinical care)

1. Daily non-respiratory SOFA score

2. Daily creatinine
3. Daily lactate
4. Presence of acute respiratory distress syndrome
5. Stage II or greater AKI by KDIGO criteria

Exploratory Safety Outcomes:

1. Atrial arrhythmia
2. Ventricular arrhythmia
3. Cardiac arrest
4. Pneumothorax or pneumomediastinum
5. Ischemic stroke
6. Myocardial infarction

Measures of Separation between Groups:

1. SpO₂
2. SaO₂
3. FiO₂
4. PaO₂
5. Episodes of hypoxemia, including:
 - a. SpO₂ < 85% for ≥ 5 minutes
 - b. SpO₂ < 80% for ≥ 5 minutes
 - c. SpO₂ < 70% for ≥ 2 minutes
6. Episodes of hyperoxemia, including:
 - a. SpO₂ > 98% for ≥ 5 minutes
 - b. SpO₂ > 98% for ≥ 30 minutes
7. Proportion of patients with a value for PaO₂ < 55 mm Hg
8. Proportion of patients with a value for PaO₂ > 120 mm Hg

Exploratory Processes of Care Outcomes:

1. Tidal volume
2. Positive end expiratory pressure
3. Peak airway pressure
4. Receipt of mandatory ventilator mode
5. Number of arterial blood gasses
6. Hemoglobin
7. Red cell transfusion

8.0 Risks and Benefits:

Among adult patients for whom the treating clinicians have decided invasive mechanical ventilation is required, there are currently no established risks or benefits to targeting a higher, intermediate, or lower SpO₂. At this time, there is no reason to

believe that participation in this study would expose patients to greater medical risks or benefits than those experienced by critically ill patients receiving invasive mechanical ventilation as a part of routine care. The greater benefit of the study would be to society in the form of improved understanding of safe and effective provision of oxygen therapy during mechanical ventilation for critically ill patients.

A potential risk to patients participating in this study involves the collection of protected health information (PHI). In order to limit the associated risks, the minimum amount of PHI necessary for study conduct will be collected. After collection, the data will be stored in a secure online database (REDCap) only accessible by the investigators. After publication, a de-identified database will be generated to protect participant privacy.

9.0 Safety Monitoring and Adverse Events:

9.1 Safety Monitoring

The PILOT trial will take place in a high-acuity clinical care environment during delivery of a high-acuity procedure required for routine clinical care. During the time of the study intervention, the patient will have a critical care or emergency medicine nurse with a low patient-to-nurse staffing ratio, immediate access to a respiratory therapist, and a team of critical care physicians physically located on the study unit twenty-four hours a day. As a part of routine care all patients will be receiving continuous invasive or non-invasive monitoring of heart rate, blood pressure, respiratory rate, and oxygen saturation.

Study personnel will monitor compliance with the study inclusion and exclusion criteria, study protocol, and study safety measures daily. Study personnel will be readily available to answer questions at any time from patients, legally authorized representatives, or treating clinicians. If, at any point in a patient's clinical course, the treating clinicians believe an SpO₂ target different from the assigned target is required for the safe treatment of the patient, the SpO₂ target will be modified to the target the treating clinicians judge to be safest.

A structured plan for prospective collection of study outcomes has been specified, in addition to a process by which Adverse Events and Serious Adverse Events will be managed and reported as required to regulatory bodies.

A Data and Safety Monitoring Board (DSMB) will be appointed to oversee the study. The DSMB will be available throughout the trial to monitor enrollment, protocol compliance, safety, and adverse events. Additionally the DSMB will perform an interim analysis for safety and efficacy.

9.2 Adverse Event Reporting

A system has been established to report and track clinical outcomes and adverse events (AEs). Study personnel will monitor the safety of subjects and follow AEs until the event resolves or is explained.

Clinical Outcomes (not considered Adverse Events). In this study of critically ill patients who are at high risk for death or other adverse outcomes due to their underlying critical illness, clinical outcomes, including death and organ dysfunction, will be systematically tracked (collected in the case report form) and will be included as part of the analyses for this study. For the purposes of reporting, death and organ dysfunction will not be recorded as AEs unless the investigator believes the event may have been caused by the study or is more severe or prolonged than expected given the underlying critical illness. This approach—considering death and organ dysfunction as outcomes rather than AEs and systematically tracking expected outcomes for analysis rather than solely recording individual AEs—is common in ICU trials because these outcomes/events occur commonly in the ICU and this system mandates that data regarding death, organ dysfunction, and expected outcomes be tracked systematically for all patients and analyzed appropriately. Clinical outcomes will be systematically tracked throughout the study period. Listed below are events that will be tracked as primary, secondary, or exploratory clinical outcomes and will not therefore be reported as AEs during this study (unless believed to be study related and more severe or prolonged than expected given the underlying critical illness):

1. Death (all deaths occurring prior to hospital discharge will be reported on the CRF in the vital status at hospital discharge section);
2. Recurrence of respiratory failure, including need for re-intubation or non-invasive mechanical ventilation, presence of acute respiratory distress syndrome, or presence of pneumothorax or pneumomediastinum;
3. Circulatory failure, including cardiac arrest or shock with or without receipt of vasopressors;
4. Incidence of sustained atrial and ventricular arrhythmias;
5. Acute kidney injury, including leading to increased creatinine or receipt of renal replacement therapy;
6. Hepatic injury or failure leading to increased bilirubin, AST, or ALT;
7. Coagulation derangements leading to elevated PT/INR or PTT, DIC, thrombocytopenia, or thrombocytosis;
8. Lactic acidosis;
9. Delirium, disability, and physical or cognitive impairment believed to be newly acquired;
10. All values for SpO₂, SaO₂, FiO₂, PaO₂, or PaO₂/FiO₂ ratio;
11. All values for vital signs (e.g., temperature, respiratory rate, SpO₂);
12. Receipt of co-interventions (e.g., number of arterial blood gasses, red cell transfusion)

13. Duration of ICU admission, ICU readmission;
14. Duration of hospitalization, hospital readmission;
15. Alterations in routine labs, including chemistries, complete blood counts, liver function tests, and hemostasis profiles.

Adverse Event Classifications. An Adverse Event (AE) will be any untoward medical occurrence for a patient enrolled in the trial that is not tracked as a clinical outcome, regardless of whether the event is considered study related or not. All AEs occurring during the observational study period will be recorded on the CRF. All AEs will then be assessed as to whether they are (1) related to study procedures, (2) serious, and/or (3) unexpected according to the following definitions:

- I. Related to study procedures. AEs that the investigator suspects are related to the study will be classified as study related. Certainty of relatedness is not required as long as a reasonable possibility exists that the AE is related to a study procedure.
- II. Serious. AEs that meet any of the criteria below will be considered Serious Adverse Events (SAEs):
 - a. Results in death
 - b. Is life-threatening (defined as an event in which the participant was at risk of death at the time of the event and NOT an event that hypothetically might have caused death if it would have been more severe)
 - c. Prolongs an existing hospitalization
 - d. Results in persistent or significant disability or incapacity
 - e. Results in a congenital anomaly or birth defect
 - f. Important medical event that requires an intervention to prevent any of a-e above.
- III. Unexpected. AEs that are more severe or prolonged than expected based on the investigator's discretion will be considered Unexpected.

The PILOT trial will monitor, track, and report all Clinical Outcomes and AEs as required by regulatory bodies.

Communication and Reporting of Adverse Events. In order to ensure proper and timely reporting of all adverse events, there will be a clear communication plan for all study personnel to follow. AEs will be recorded in the AE CRF in the electronic database and reported to the PI within 5 days of occurrence. The PI will provide a report of all AEs annually to the IRB and DSMB as part of the annual review process as required. All SAEs will be reported to the PI within 72 hours of occurrence. The PI will, in turn, report all SAEs to the IRB, DSMB, and funding body within 7 calendar days of occurrence.

9.3 Frequency of Monitoring and Interim Analysis.

Study personnel will continuously monitor enrollment, protocol compliance, and AEs and SAEs throughout the course of the trial. Semi-annually, the DSMB will formally review enrollment, protocol compliance, and AEs and SAEs as part of a formal DSMB meeting. Additionally, the DSMB will be available to convene a meeting at any point in the course of the trial to review urgent issues related to AEs, protocol compliance, or unexpected adverse events. Study personnel and DSMB members will adhere to the expectations for reporting and managing AEs and unexpected adverse events outlined in the DSMB charter.

Interim Analysis. In addition to ongoing monitoring of safety throughout the trial, the DSMB will conduct a single interim analysis for efficacy and safety at the anticipated halfway point of the PILOT trial. The interim analysis will include patients enrolled during the first 18 months of the trial. The stopping boundary for efficacy will be met if the P value for the difference between groups is <0.001 . Use of the conservative Haybittle-Peto boundary ($P < 0.001$) will allow the final analysis to be performed using an unchanged level of significance ($P = 0.05$). Given the minimal risk nature of the study and current use of all SpO_2 target as a part of usual care, there will be no stopping boundary for futility. The DSMB will reserve the right to stop the trial at any point, request additional data or interim analyses, or request modifications of the study protocol as required to protect patient safety.

9.4 Data and Safety Monitoring Board (DSMB). A formal independent DSMB will oversee the conduct of the trial and the planned interim analysis. The DSMB will be composed of at least one physician outside the study institution experienced in the conduct of critical care clinical trials and one biostatistical expert who will assist with study monitoring and performance of the interim analysis.

9.5 Data Monitoring Plan. To ensure data are accurately and completely collected during the PILOT trial, the study team will follow a specific Data Monitoring Plan. All clinical outcomes will be collected in duplicate by both electronic data collection and by the study nurse. All study data from random sample of 10% of study records will be collected in duplicate by electronic data collection and by the study nurse. Each of these records will also be reviewed annually by the primary investigator to ensure data collection is accurate, complete, and current. The study biostatistician will run periodic data cleans throughout the study looking for outliers or overtly erroneous data. This Monitoring Plan will serve as a method for identifying and resolving systematic problems and therefore increase data quality. We will submit progress reports to the local IRB annually, or more frequently if requested.

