13.0 Follow-up and Record Retention

Patients will be followed after enrollment for 28 days or until hospital discharge, whichever occurs first. Data collected from the medical record will be entered into the

Principal Investigator: [name]

Version Date: 4/7/2021

Study Title: Pragmatic Investigation of optimal Oxygen Targets (PILOT) Trial

Institution: Vanderbilt University Medical Center

secure online database REDCap. Once data are verified and the database is locked, all hard copies of data collection forms will be destroyed. All data will be maintained in the secure online database REDCap until the time of study publication. At the time of publication, a de-identified version of the database will be generated.

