At the conclusion of the closed and executive sessions, the participants will be re-convened so that the DSMB Chair can provide a summary of the DSMB's recommendations. This provides an opportunity for study investigators to ask questions to clarify the recommendations. The meeting is then adjourned.

7. Expedited Safety Reporting

A system has been established to track and report adverse events (AEs). Study personnel will monitor the safety of subjects and follow AEs until the event resolves or is explained.

Clinical Outcomes (not considered Adverse Events). In this study of critically ill patients who are at high risk for death or other adverse outcomes due to their underlying critical illness, clinical outcomes, including death and organ dysfunction, will be systematically tracked (collected in the case report form) and will be included as part of the analyses for this study. For the purposes of reporting, death and organ dysfunction will not be recorded as AEs unless the investigator believes the event may have been caused by the study or is more severe or prolonged than expected given the underlying critical illness. Listed below are events that will be tracked as primary or secondary clinical outcomes and will not therefore be reported as AEs (unless believed to be study related and more severe or prolonged than expected given the underlying critical illness):

1. Death (all deaths occurring prior to hospital discharge will be reported on the CRF in the vital status at hospital discharge section);
2. Recurrence of respiratory failure, including need for re-intubation or non-invasive mechanical ventilation, presence of acute respiratory distress syndrome, or presence of pneumothorax;
3. Circulatory failure, including cardiac arrest or shock with or without receipt of vasopressors;
4. Incidence of sustained atrial and ventricular arrhythmias;
5. Acute kidney injury, including leading to increased creatinine or receipt of renal replacement therapy;
6. Hepatic injury or failure leading to increased bilirubin, AST, or ALT;
7. Coagulation derangements leading to elevated PT/INR or PTT, DIC, thrombocytopenia, or thrombocytosis;
8. Lactic acidosis;
9. Delirium, disability, and physical or cognitive impairment believed to be newly acquired;
10. All values for SpO₂, SaO₂, FiO₂, PaO₂, or PaO₂/FiO₂ ratio;
11. All values for vital signs (e.g., temperature, respiratory rate, SpO₂);

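### Section 9.2 exempts 15 event types from AE reporting as tracked outcomes, but delirium and disability, and components of eight other items, are in no outcome list, and severe hypoxaemia is only a measure of separation

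*Combined protocol and SAP*

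**What the plan says.** Protocol v1.5 section 9.2 argues that in critically ill patients, death and organ dysfunction are better followed systematically as outcomes in every patient than recorded one by one as AEs. It then gives a numbered list of 15 event types under the sentence "Listed below are events that will be tracked as primary, secondary, or exploratory clinical outcomes and will not therefore be reported as AEs". The sentence goes on to except events believed to be study related and more severe or prolonged than the underlying illness would explain. The same section defines an AE as an untoward occurrence that is not tracked as a clinical outcome.

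Three of the listed items are:
- item 7: "Coagulation derangements leading to elevated PT/INR or PTT, DIC, thrombocytopenia, or thrombocytosis"
- item 9: "Delirium, disability, and physical or cognitive impairment believed to be newly acquired"
- item 14: "Duration of hospitalization, hospital readmission"

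Item 10 exempts every SpO₂, SaO₂, FiO₂ and PaO₂ value and the PaO₂/FiO₂ ratio. Item 15 exempts changes in routine laboratory tests, including liver function and haemostasis profiles.

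Section 7.4 places episodes of hypoxaemia (SpO₂ below 85% or below 80% for at least 5 minutes, below 70% for at least 2 minutes) under "Measures of Separation between Groups", as items 5a to 5c. The Exploratory Safety Outcomes are a separate list of six events that does not include them. On follow-up, section 13.0 says: "Patients will be followed after enrollment for 28 days or until hospital discharge, whichever occurs first".

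DSMB charter section 7 repeats the exemption, with the same exception, in slightly different terms: "Listed below are events that will be tracked as primary or secondary clinical outcomes and will not therefore be reported as AEs".

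**The concern.** The exemption is reasonable only where its premise is true: an event may be left off the AE forms because it will be counted and compared as an outcome. Where an exempt event is not an outcome, neither route gives a planned comparison between targets. It also falls outside SAE reporting, because an SAE must first be an AE, unless an investigator judges that the exception applies. The overlap is sharpest for item 9: disability is exempt, while persistent or significant disability is one of the SAE criteria in the same section.

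Hypoxaemia matters most. Section 2.0 says lower targets may increase the risk of hypoxaemia, tissue hypoxia and organ dysfunction. A desaturation episode in the lower arm is therefore both evidence that the intervention was delivered and a possible harm of it. The plan classifies it only as the first.

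**Working it through.** No sample-size or error-rate figure is involved. The check sets each of the 15 items in section 9.2 beside the section 7.4 lists, and then beside the data elements in section 7.3 and in section 18 of the SAP supplement.

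**Items matched in 7.4 (6):** 1 death; 3 circulatory failure (cardiac arrest, vasopressor-free days, SOFA); 4 arrhythmias; 5 acute kidney injury; 8 lactic acidosis (daily lactate); 12 co-interventions (blood gases, red cell transfusion).

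**Items with a component in no 7.4 list (9):**

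| Item | What 7.4 covers | What it does not cover |
|---|---|---|
| 2 Recurrent respiratory failure | Re-intubation (through VFDs), ARDS, pneumothorax or pneumomediastinum | Need for non-invasive ventilation |
| 6 Hepatic injury | Bilirubin, only inside the non-respiratory SOFA score | AST, ALT (extracted, but not an outcome) |
| 7 Coagulation | Low platelets, only inside SOFA | PT/INR, PTT, DIC; thrombocytosis (counts above 150 score 0 in Table S1) |
| 9 Delirium, disability, impairment | Nothing | The whole item |
| 10 Oxygenation values | SpO₂, SaO₂, FiO₂, PaO₂, only as separation measures | PaO₂/FiO₂ ratio |
| 11 Vital signs | SpO₂, as a separation measure; mean arterial pressure, through SOFA | Temperature, respiratory rate and others |
| 13 ICU stay | ICU-free days | ICU readmission as an event |
| 14 Hospital stay | Hospital-free days | Hospital readmission |
| 15 Routine laboratory changes | Creatinine, lactate, haemoglobin; bilirubin and platelets through SOFA | Other chemistries, AST/ALT, haemostasis profiles |

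The count is 6 matched + 8 matched in part + 1 unmatched = 15, so 8 + 1 = 9 items have at least one component in no list.

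**Whether the data exist for the unmatched components:**
- CAM-ICU scores, bilirubin, AST, ALT and platelets are in the automated extraction (SAP supplement section 18). SpO₂ is archived every 60 seconds (protocol section 7.1).
- PT/INR and PTT are in neither laboratory list.
- Readmission after discharge falls outside follow-up (section 13.0).
- Cognitive and physical outcomes at 12 months belong to the separately funded and separately consented CO-PILOT study, not to this trial's outcome lists.

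**Hypoxaemia.** Item 10 exempts the values. Episodes 5a to 5c are in 7.4, but not under a heading labelled primary, secondary or exploratory. The exploratory families named in sections 1.0 and 3.0 are clinical, organ function and safety only. Section 11.0, under Analysis of the Exploratory Outcomes, assigns models to exploratory outcomes and does not name the separation measures. The matching SAP section does the same, and section 20 of the SAP supplement again lists the episodes as separation measures without a model.

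**Internal conflict.** By the AE definition in 9.2, an event that is not tracked as a clinical outcome is an AE. By the list, the untracked components above are not AEs. Both cannot hold.

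**The case against.** The case for leaving the plan alone has real force.

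- **The exemption is conditional.** A reader might infer that these events can never be reported. The documents do not say so: an event judged study related and worse than expected stays reportable, and if serious it goes to the IRB, DSMB and funder within 7 days. This stands. Its protection is limited, because it depends on an investigator's judgement in an un-blinded trial. The list sentence also requires both conditions, while the general rule earlier in the same paragraph accepts either.
- **Most items are partly covered.** It is tempting to say that items 6, 7, 9 and 14 have no matching outcome at all. That is true only of item 9. Bilirubin and platelets enter through SOFA, and hospital stay through hospital-free days. An ICU readmission within the same stay would also shorten ICU-free days, which run from the final ICU stay (SAP supplement section 19).
- **Hypoxaemia is measured well.** Three thresholds are prespecified under a heading about differences between groups, monitors alarm on out-of-range values, and clinicians may modify the target. This stands too, so what is missing is classification and a named analysis, not data.
- **The DSMB may already see these events.** A reader might infer that they do not reach the board. That cannot be shown: the charter gives the DSMB other safety data at each meeting and leaves the content of reports to its Appendix B, which is not in the text available.
- **A blunt remedy would do harm.** Restricting the exemption to 7.4 outcomes would turn routine vital-sign and laboratory changes into AEs in a planned 2,250 ventilated patients. Deleting PT/INR and PTT from item 7 alone would achieve nothing, because item 15 still exempts haemostasis profiles.

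**Conclusion.** The point holds in a limited form. The reason given for the exemption is untrue for one whole item of 15 (item 9) and for components of eight others, 9 of 15 in all. Not all nine carry equal weight: missing vital signs and routine chemistries are of little consequence, whereas delirium, liver enzymes, coagulation and disability are events that a safety reader would expect either to be reported or to be compared.

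The more important part is hypoxaemia. The plan names it as a risk of lower targets, exempts it from AE reporting, and specifies no between-group safety analysis for it by name.

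This rests on reading 7.4 as the complete outcome list, and on the absence of a named analysis for the separation measures in the protocol, the SAP and its supplement. It does not establish that harm would go unnoticed, that events are withheld from the DSMB, or that the general approach of tracking expected ICU events as outcomes is wrong.

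**What to change.** 1. List hypoxaemia episodes 5a to 5c also as Exploratory Safety Outcomes, keeping them as separation measures, and analyse them as set out under Analysis of the Exploratory Outcomes. Confirm that they are in the by-arm DSMB reports.
2. Add by-arm summaries of delirium (CAM-ICU) and of bilirubin, AST, ALT and platelets from the data already extracted. Give the number of patients assessed in each, since the laboratory tests come from routine care and CAM-ICU is deferred in unresponsive patients.
3. Correct the sentence in section 9.2 and in DSMB charter section 7 so that it no longer says that untracked components (PT/INR, PTT, DIC, readmission, disability) are tracked as outcomes. Edit items 7 and 15 together. Keep routine vital-sign and laboratory changes out of AE reporting, on the stated ground that they are expected in this population rather than that they are outcomes.

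None of this needs new data collection. The cost is a few more tables and a short amendment to the protocol and charter.
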